#### 8.1.2 Secondary study parameters/endpoints

Secondary parameters will include total maximum SOFA score (= total of the most deranged score of each organ system during ICU stay), total maximum SOFA score - SOFA score on admission, SOFA rate of decline, hypoxic episodes ( $PaO_2 < 55 \text{ mmHg}$ ), vasopressor / inotrope requirements (max dose every 24 hours), need for renal replacement therapy and fluid balances (every 24 hours). Furthermore, oxidative stress parameters F2-isoprostanes will be determined (on days 1, 2 and 4) and as clinical endpoints: duration of mechanical ventilation, ventilator-free days, length of stay (in ICU, in hospital) and mortality (ICU and hospital). Interim analyses will take place after inclusion of 100 patients to detect possible differences in mortality.

The amount, modality and duration of oxygen administered prior to ICU admission will be recorded. This will be treated as a potential effect-modifying variable and reported in the baseline characteristics.

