#### **10. STATISTICAL ANALYSIS**

#### **10.1 Descriptive statistics**

Statistical analysis will be performed using the SPSS statistical software package (SPSS Inc.®, Chicago USA). All included patients will be incorporated in the statistical analysis. Descriptive statistics of these quantitative data will include mean, median, standard deviation and interquartile range.

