## 10.2 Primary and secondary study parameter(s)

#### **Calculations of CDDS primary endpoint**

The primary endpoint will be *cumulative daily delta SOFA score* (CDDS) from day 1 to day 14, calculated as:

$$CDDS = \sum_{i=day2to14} (SOFA_{DAYi} - SOFA_{ADMISSION})$$

or alternatively,

$$CDDS = SOFA_{DAY2} + SOFA_{DAY3} + SOFA_{DAY4} + \dots etc + SOFA_{DAY14} - (13 \cdot SOFA_{ADMISSION})$$

Daily SOFA score is calculated as the total of maximum scores for each organ system excluding respiratory system (because of possible PaO2/FiO2 distortion). For patients discharged from the ICU, SOFA score will be registered as 0 from the day of discharge to day 14. Death in the ICU will be registered as a score of 20 (maximum) from the day of death to day 14.

CDDS reflects a balanced weighting of the following clinically relevant preconditions:

- 7. Low (or negative) delta SOFA score is better than high (or positive) delta SOFA score.
- 8. Shorter duration of ICU stay is better than longer stay.
- 9. Discharge from the ICU is better than death in the ICU.
- 10. Eventual discharge after a high admission SOFA score is better than discharge after a low admission SOFA score.
- 11. Eventual death after a low admission SOFA score is worse than discharge after a high admission SOFA score.
- 12. Early SOFA score reduction is better than late SOFA score reduction.

Other possible endpoints (such as *delta SOFA score* or *SOFA rate of decline*) fail to satisfy most of these criteria.

The differences of primary and secondary parameters between the 2 groups will be calculated by intention-to-treat analysis. The primary endpoint (CDDS) is designed and

tested as a tool for ranking outcomes. The between-group comparison on the primary endpoint will therefore be made using the Wilcoxon rank-sum test.

Secondary outcomes will be compared using ANOVA for repeated measurements, Chi-Squared, Mann-Whitney U or Fisher's Exact test where appropriate. Mortality will be assessed with the Kaplan Meier and log rank test.

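### The only method listed for serial secondary outcomes, repeated-measures ANOVA, in its standard form loses patients who die or leave the ICU before the last time point

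*Supplement*

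**What the plan says.** Section 10.2 of the final protocol covers the analysis of all secondary outcomes, apart from the survival analysis of mortality, in one sentence: "Secondary outcomes will be compared using ANOVA for repeated measurements, Chi-Squared, Mann-Whitney U or Fisher's Exact test where appropriate". It does not say which test goes with which outcome.

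Several of these outcomes are serial. Section 8.1.2 lists vasopressor and inotrope "requirements (max dose every 24 hours), need for renal replacement therapy and fluid balances (every 24 hours"), and F2-isoprostanes that "will be determined (on days 1, 2 and 4"). Section 8.1.4 adds substudy measurements on days 1, 2 and 4: sublingual microcirculation, bio-impedance and diaphragm function.

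Two statements define who is analysed. Section 10.1: "All included patients will be incorporated in the statistical analysis". Section 10.2: "The differences of primary and secondary parameters between the 2 groups will be calculated by intention-to-treat analysis".

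For software the plan says "Statistical analysis will be performed using the SPSS statistical software package" and names no procedure. Section 10.2 gives values after ICU discharge (0) and ICU death (20), but for the SOFA score only. For the other serial outcomes there is no rule for values after exit, no analysis window, no imputation and no mixed model.

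**The concern.** Chi-squared, Mann-Whitney and Fisher's test each need one value per patient. If a serial outcome is analysed as a series, repeated-measures ANOVA is the only listed choice. The standard version requires a complete row and drops any patient with one gap.

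Gaps are foreseeable. Entry requires only a predicted stay above 48 hours (section 5.2), so some patients can die or be discharged before day 4. Blood is taken from lines used in ICU care (Summary), and no sampling after ICU discharge is described. The patients left in the ANOVA would be those alive and still in the ICU at the last time point, a group formed after randomisation by how patients fared.

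F2-isoprostanes are the only named marker for the Summary's objective on oxidative stress, and a lower vasopressor need is one of the benefits proposed for hyperoxia. Early values from patients who leave would be discarded. ICU mortality and length of stay are themselves trial outcomes, so membership of the complete-row group may depend on the assigned target.

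**Working it through.** **The plan's own figure.** The plan states no sample size or power for the serial outcomes. Its one figure, 385, belongs to the primary endpoint (section 5.4: 0.33 SD, 90% power, two-sided 5%). With 1:1 allocation (assumed), n per arm = 2(1.960 + 1.282)²/0.33² ≈ 193, total 386. This agrees with 385. Simulating the stated interim bounds at 150, 275 and 385 patients gives a type I error of 0.0497 and power of 0.895. This confirms the 385 and has no bearing on the serial outcomes.

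**Loss of complete rows.** Let h be the share of patients leaving each day by death or discharge. The documents give no value; 3% to 12% is assumed. A row complete from day 1 to day d needs d − 1 days without exit, so complete rows = 385 × (1 − h)^(d − 1). Power to detect a difference of 0.33 SD, borrowed from the primary endpoint as a yardstick, is Φ(0.33 × √(m/4) − 1.96), with m the number of complete rows. With all 385 rows it is 0.90.

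| Exits per day | Complete by day 4 | Power | Complete by day 7 | Power | Complete by day 14 | Power |
|---|---|---|---|---|---|---|
| 3% | 351 (91%) | 0.87 | 321 (83%) | 0.84 | 259 (67%) | 0.76 |
| 8% | 300 (78%) | 0.82 | 233 (61%) | 0.71 | 130 (34%) | 0.47 |
| 12% | 262 (68%) | 0.76 | 179 (46%) | 0.60 | 73 (19%) | 0.29 |

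For 3%: 385 × 0.97³ = 385 × 0.913 = 351. For 12%: 385 × 0.88³ = 385 × 0.681 = 262. The loss by day 4 is thus 9% to 32%. The day 7 and day 14 columns apply only if the daily outcomes were analysed over those windows, which the plan does not fix.

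**Bias.** This was simulated with 385 patients, three visits and 4,000 runs. All inputs are assumed. Each value is 0.8 × severity + 0.6 × noise, so a single measurement has SD 1. Sicker patients tend to die and healthier ones tend to be discharged before day 4; the base rates are 10% dead and 20% discharged. The test compares the arms on the mean of the three visits among complete rows.

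| Exits in one arm relative to the other | True difference | Rows kept | Difference in complete rows | Share significant |
|---|---|---|---|---|
| Equal | 0 | 70% | 0.00 | 0.051 |
| 5 points more deaths | 0 | 68% | −0.05 | 0.085 |
| 10 points fewer discharges | 0 | 75% | −0.10 | 0.22 |
| 5 points more deaths, 10 points fewer discharges | 0 | 73% | −0.15 | 0.44 |
| 5 points more deaths, 10 points more discharges | 0 | 63% | +0.04 | 0.067 |
| Equal | 0.25 | 70% | 0.25 | 0.85 |
| 5 points more deaths, 10 points fewer discharges | 0.25 | 73% | 0.10 | 0.23 |

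With equal exits the error rate holds and only patients are lost. In the fourth row the arm with the worse course appears lower on the marker, because death removes its sickest patients and fewer of its healthier ones go home. In the fifth row the two forces nearly cancel.

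**The case against.** The strongest reply is that the plan never says it will analyse complete rows only. SPSS is named without a procedure, and the sentence on secondary outcomes leaves the choice of test to what is appropriate. A daily series could be reduced to one value per patient and compared by Mann-Whitney. Section 8.1.4 does plan areas under the curve for PaO2, saturation, FiO2 and lactate. Intention-to-treat may mean no more than analysis by assigned group. Section 10.1's sentence on all included patients stands under descriptive statistics. A discharged patient's vasopressor dose could be entered as zero, in line with the SOFA rule, so that only death would cut that series short.

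Part of this stands. Row deletion is a property of the named method in its standard form, not a statement in the protocol, and every percentage above rests on assumed exit rates. But no single-value summary is planned for vasopressor dose, fluid balance or F2-isoprostanes, and the SOFA rule is not extended to them. The wording on all included patients is general. Followed in the ordinary way, the plan loses these patients.

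A further fair point is that a mixed model alone does not deal with death. It keeps the early values but treats values after death as if they existed and were merely unobserved.

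**Conclusion.** The concern holds for the serial secondary outcomes: F2-isoprostanes, daily vasopressor dose and fluid balance, and the day 1, 2 and 4 substudy measures. The only repeated-measures method listed does not, in its standard form, fit the commitment to analyse all included patients by intention-to-treat when rows are incomplete. The illustrative loss is about 9% to 32% of patients by day 4, at an assumed 3% to 12% exits per day.

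A reader might infer that the plan commits itself to a complete-row analysis. It does not; that follows from the method named, and the SPSS procedure is left open. A reader might also infer that the results would be biased. That needs exits that differ between arms, which is plausible but not established; with equal exits the cost is power.

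The primary endpoint has its own values for death and discharge and a rank test, and is unaffected. So are the single-value secondary outcomes, such as maximum SOFA, length of stay, ventilator-free days and mortality. The change is worth making but does not touch the main conclusion of the trial.

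**What to change.** In section 10.2, replace repeated-measures ANOVA for the serial outcomes by a linear mixed model, which SPSS offers, using all available measurements with treatment, day and treatment-by-day. Use the day 1 value either as a covariate, with outcomes from day 2, or as part of the outcome series, but not both. Section 8.3 describes the first blood sample as baseline, so the double use is easy to make.

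Also:
- fix the analysis window for the daily outcomes in advance;
- state, outcome by outcome, which values after ICU discharge count as zero and which as missing;
- report the number of patients contributing per arm and day;
- because the mixed model does not handle death, add as a sensitivity analysis a patient-level rank comparison with death ranked worst.

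The cost is a few sentences in the plan and a little more analysis work, with no new data, visits or patients.

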#### 10.3 Interim analysis (if applicable)

Interim analyses (blinded for the intervention arm) will take place after inclusion of 150 and 275 patients to detect possible differences in mortality.

The interim analyses are planned as a symmetric two-sided group sequential design with 90% power and 5% two-sided Type I Error. Spending computations assume the trial stops if a bound is crossed.

Analysis	Ν	Boundary	Spend
		two-sided P	
1	150	0.0006	0.0006
2	275	0.0156	0.0152
3	385	0.0452	0.0342
total			0.050

++ alpha spending:

Lan-DeMets O'brien-Fleming approximation spending function

For example, the trial will be stopped after 275 patients if there is a sufficient difference in primary endpoint between the two groups, such that P<0.0156.

In addition to the trial stopping boundaries for superior outcomes in one of the trial arms (outlined above), we have defined a futility stopping boundary at interim-analysis 2 (after N=275 patients): The trial will be stopped if there is almost no difference in the primary endpoint between the treatment arms, such that the conditional power is less than 20% at interim-analysis 2. Practically, if P>0.459 after 275 patients, there is a less than 20% probability of obtaining a significant result after 385 patients.

The METc/CRB will be consulted when, at the interim analysis, between-group differences in mortality are large enough so that P<0.05 but not large enough to reach one of the stopping criteria outlined above.

#### **11. ETHICAL CONSIDERATIONS**

#### **11.1 Regulation statement**

The study will be conducted according to the principles of the Declaration of Helsinki (59th WMA General Assembly, Seoul 2008) and in accordance with the Medical Research Involving Human Act (WMO) and the statements of the CCMO as presented in the publication "Uitgestelde toestemming voor inclusie van beslissingsonbekwame patiënten in studies van spoedeisende geneeskunde" by E.J.O.Kompanje.

#### 11.2 Recruitment and consent

#### 11.2.1. Deferred consent

For this study we ask for deferred consent and we appeal to the emergency procedure for consent in medical research as stated in article 6, paragraph 4 of the WMO because of the following reasons.

Oxygen suppletion is applied to almost all ICU-patients. To alleviate respiratory distress oxygen therapy is initiated and cannot be postponed. Patients admitted to an Intensive Care Unit (ICU) are mostly incompetent to give informed consent. Obtaining informed consent from a legal representative takes time (on average up to 12 hours), even by an experienced research team.

We propose to randomize each patient who meets the inclusion criteria ultimately within 2 hours after ICU admission. Oxygenation targets according to randomization are applied immediately thenceforth. Informed consent from the legal representative will be requested as soon as possible thereafter, but never later than 24 hours after randomization. If informed consent is not obtained within those 24 hours, or if a legal representative denies participation within this time frame, the patient is excluded and data will no longer be used. Thenceforth the patient is oxygenated according to the policy of the attending physician.

During hospital admission, we will attempt to achieve informed consent from the patients themselves. If this was not possible (*for example* due to incomplete neurological or physical recovery, or due to early transfer to another hospital) we will send a letter to the patients to inform them that we would like to use the data and blood samples obtained during the study. If they don't want their data to be used, they can contact us by the telephone numbers or email addresses we have provided in the letter. We will not send this letter to the patients who cannot recover sufficiently to understand the letter and take a considered decision about the study.

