#### 5.4 Sample size calculation

Power calculations are based on mean delta SOFA scores, which are invariably reflected in CDDS.

The trial is designed to detected a difference of 0.33 standard deviation (SD) on the primary endpoint with 90% power and a 2-sided alpha of 0.05, with 2 interim analyses.

The trial will be stopped if there is evidence for outcome differences in either direction. Alpha

spending for the interim analyses is approximated with a Lan-DeMets O'Brien-Fleming

spending function. The total sample size thus needed is 385 patients.

Hyperoxia and SIRS ("O2-ICU")

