#### 11.2.3. Time between asking for and obtaining informed consent

Most critically ill patients cannot give informed consent for a study at ICU admission. They are in severe respiratory distress, sedated or in coma. Time to obtain informed consent after recognition of study eligibility by a legal representative could take as much as 12 hours, even when a legal representative could be contacted fast. This is in line with a recent observational study performed in the Academic Medical Center, Amsterdam, the Netherlands. Time to obtain informed consent after recognition of study eligibility from a legal representative was as high as 14 hours (study ID NL34294.018.10). For relatives of a severely ill patient who has been acutely admitted to the ICU it is difficult to make a quick, but balanced decision. 

Most ICU patients are positive about their enrollment under deferred consent. A contentment questionnaire of the large NICE–SUGAR trial , a trial studying different targets in blood glucose control , showed that the large majority (96%) would have granted consent if they would have been asked. 93% of the patients were content with the decision made by the representative at the moment they were incapable of giving informed consent. 

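### Randomised, already treated patients are dropped with their data if consent is not in hand within 24 hours, which conflicts with the promised intention-to-treat analysis and can bias CDDS and mortality

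*Supplement*

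**What the plan says.** All references are to the final protocol in the Supplement, whose section 10 is the analysis plan.

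- **Section 11.2.1 (Deferred consent).** Patients are randomised within 2 hours of ICU admission and the assigned target is applied at once. The representative is asked afterwards, with a limit of 24 hours from randomisation. Both a refusal and the mere absence of consent at 24 hours have the same result: "the patient is excluded and data will no longer be used". Death before the limit is not mentioned. The later provisions on patient consent and the information letter do not bring these patients back.
- **Section 10.2.** "The differences of primary and secondary parameters between the 2 groups will be calculated by intention-to-treat analysis". ICU death is scored 20 from the day of death to day 14.
- **Section 10.1.** "All included patients will be incorporated in the statistical analysis". The word for who counts as included is not defined.
- **Section 11.2.3.** On the time consent takes, one earlier study at a participating centre is cited: "Time to obtain informed consent after recognition of study eligibility from a legal representative was as high as 14 hours". Section 11.2.1 gives an average of up to 12 hours.
- **Section 5.4.** The target is "a difference of 0.33 standard deviation (SD) on the primary endpoint", "with 90% power and a 2-sided alpha of 0.05, with 2 interim analyses", and then "The total sample size thus needed is 385 patients". There is no allowance for consent loss and no statement of whether 385 is a randomised or an analysed count.
- **Section 8.2** describes a randomisation list and no blinding.

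**The concern.** An intention-to-treat comparison keeps every randomised patient in the assigned arm. The consent rule takes some of them out after allocation and after the target has been applied. Explicit refusal may leave no choice. But the rule also removes patients whose representative was not found, or had not decided, in time. A patient who dies on the first day before a representative is reached falls in that group.

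Two features make this more than a matter of labelling. First, removal can depend on early outcome, and early outcome may depend on the arm: section 11.2.2 itself says that circulatory effects of hyperoxia appear within an hour, or even within 10 minutes. Second, with no blinding described, staff and representatives may know the assigned target when consent is sought. Losses could therefore differ between arms in number or in kind. The primary endpoint would be affected, and so would mortality, which the interim analyses in section 10.3 are meant to watch.

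**Working it through.** **1. The two rules side by side.** Order of events in 11.2.1: randomise, apply the target, seek consent, then at 24 hours exclude and discard if there is none. Analysis rule in 10.2: intention-to-treat, unqualified. A treated patient with no consent at 24 hours must be left out under the first and kept in under the second. Section 10.1 does not settle it, because an undefined included set could mean either.

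**2. What an early death contributes to CDDS.** CDDS is the sum over days 2 to 14 of daily SOFA minus admission SOFA, that is, 13 terms. A patient who dies in the ICU on day 1 or day 2 scores 20 on all 13 days:

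CDDS = 13 × (20 − admission SOFA).

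Because 20 is the cap, this is the highest CDDS possible for that admission score. It is not always the highest in the trial. With admission SOFA 15 it is 13 × 5 = 65, while a survivor admitted at 4 who stays at 10 scores 13 × 6 = 78. Early deaths thus tend to rank badly, but not automatically worst.

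**3. How an unequal loss could act (illustration, all inputs assumed).** No true effect, 192 patients per arm, normal data, rank-sum test at 0.05, and the 12 highest-ranking outcomes (about 3%) removed in total. By simulation:

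| Removed, arm A / arm B | False-positive rate |
|---|---|
| none | just under 5% |
| 4 / 8 | 7–8% |
| 3 / 9 | 9–10% |
| 0 / 12 | about 19% |

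This puts the removed patients at the extreme of the ranking, which step 2 shows is not guaranteed, so it leans to the high side. It shows the mechanism and is not an estimate for this trial.

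**4. The plan's sample size.** Inputs from 5.4: 0.33 SD, two-sided alpha 0.05, power 90%; 1:1 allocation assumed.

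- Fixed design: N = 4 × (1.96 + 1.2816)² / 0.33² = 385.9, or 193 per arm, 386 in all. The stated 385 is reproduced as a number analysed.
- Fixed-design power at 385: Φ(0.33 × √(385/4) − 1.96) = 89.9%.
- With looks at 150, 275 and 385 and boundaries P = 0.0006, 0.0156 and 0.0452 (10.3), multivariate normal integration returns spends of 0.0006, 0.0152 and 0.0342, as in the plan's table, and power of 89.5%.

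**5. Power if 385 counts randomised patients.** The loss rate d is an assumption. Analysed N = 385 × (1 − d), with the interim looks scaled likewise. The number to randomise so that 385 remain is 385 / (1 − d).

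| d | Analysed | Power, plan's boundaries | Randomise to keep 385 |
|---|---|---|---|
| 0 | 385 | 89.5% | 385 |
| 2% | 377 | 88.9% | 393 |
| 5% | 366 | 87.9% | 406 |
| 10% | 346 | 86.2% | 428 |
| 20% | 308 | 82.0% | 482 |

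If 385 counts patients with usable data, power stays at 89.5% whatever d is. These figures treat the comparison as one of means, as 5.4 does. The efficiency of the rank-sum test is a separate matter and is left out.

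**6. Can d be read from the consent times?** Only by assuming a distribution. If time to consent is exponential with mean 12 or 14 hours, the share beyond 24 hours is exp(−24/12) = 13.5% or exp(−24/14) = 18.0%. If the same figures are 90th percentiles of an exponential, it is 0.1^(24/12) = 1.0% or 0.1^(24/14) = 1.9%. The protocol's wording does not choose between these.

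**The case against.** The strongest reply is that deferred consent leaves little choice. Whether data may be kept without consent depends on the law and on the ethics guidance that the protocol invokes, which are not available here. This stands as a limit on the remedy: the METc must decide, and explicit refusals have to be respected. It does not reconcile 11.2.1 with 10.2, and it does not cover patients who died before anyone could be asked.

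A reader might infer four stronger claims that the documents do not support:

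- *That 385 leaves the trial short of 90% power.* 385 reproduces as an analysed count, and sections 10.1 and 10.3 speak of included patients and inclusion. Recruitment may simply continue until 385 have usable data. The protocol neither provides for replacement nor rules it out.
- *That a sizeable share must be lost because consent takes 12 to 14 hours.* Step 6 gives anything from 1% to 18%, depending on what those hours are taken to mean.
- *That first-day deaths always have the worst CDDS.* Step 2 shows otherwise. Entry also requires an expected stay above 48 hours, so such deaths may be few.
- *That section 10.1 promises intention-to-treat.* Only 10.2 does, and 10.1 is compatible with a consented set.

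Unequal loss between arms is possible, not shown. Continued recruitment would protect power, but it would not undo selection that depends on outcome.

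**Conclusion.** The point holds as a conflict between two stated rules with a real route to bias. Section 11.2.1 removes randomised and treated patients for a reason that can be linked to early outcome, makes no exception for early death, and is not reflected in the intention-to-treat promise of 10.2. It should be resolved, because following the consent rule as written means the analysis is not the one stated.

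The size of the bias cannot be given: the documents state neither a consent-loss rate nor an early death rate, and the direction depends on which arm loses more. The effect on power is conditional. It is nil if 385 counts patients with usable data. If 385 caps randomised patients, power with the plan's boundaries is about 89% at 2% loss, 88% at 5%, 86% at 10% and 82% at 20%, with 1:1 allocation and assumed loss rates.

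**What to change.** 1. Ask the METc to permit a minimal dataset (allocation, vital status, date of death, available SOFA) for patients who die, or whose representative is not reached, within 24 hours. Exclude only explicit refusals.
2. If the METc declines, call the primary set in 10.2 modified intention-to-treat and define it. Report exclusions by arm, by reason and, where permitted, by vital status. Add a sensitivity analysis that bounds the result by scoring unconsented early deaths as deaths; this needs at least permitted counts of such deaths by arm, with the score 13 × (20 − admission SOFA) run over a range where admission SOFA is not available.
3. In 10.1, define who is included. In 5.4 and 10.3, state whether 385, 275 and 150 count randomised patients or patients with usable data. If randomised, restate the power for an explicit loss rate or inflate to 385 / (1 − d).

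The cost is one ethics amendment, some wording in the analysis plan, a little extra analysis and a less favourable label. If 385 turns out to be a randomised count, it also means either a lower stated power or more patients.
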